### **12.2 Adjustment for Covariates**

Not applicable.

### **12.3 Handling of Missing Data**

Missing data imputation rules are described in [Section 5.2](#).

## **12.4     Multiple Comparisons / Multiplicity**

No hypothesis testing is planned.

## **13. METHODS OF EFFICACY ANALYSES**

### **13.1 Analysis of Continuous Efficacy Endpoints**

Descriptive statistics for all efficacy endpoints listed in [Section 12.1](#) will be tabulated by treatment group of the antecedent DB study. The summaries of the change from baseline results will be presented in two ways (main analysis and exploratory analysis) as specified in [Section 5.1](#).

## **14. SAFETY ANALYSES**

All safety analyses will be performed using the Safety Analysis Set. Safety summaries will be summarized using descriptive statistics by treatment group of the antecedent DB study and overall. For each continuous measure in clinical laboratory variables, vital signs, and electrocardiogram, change from baseline results will be presented in two ways as specified in Section 5.1.

### **14.1 Primary Safety Endpoints**

The primary safety endpoints are:

- Treatment-emergent adverse events (TEAEs)
- Serious adverse events (SAEs)
- Withdrawals due to adverse events (AEs)
- Potentially clinically important changes in other safety assessments

### **14.2 Adverse Events**

Adverse events will be coded using MedDRA dictionary, Version 23.0 or newer.

An AE (classified by preferred term) will be considered a treatment-emergent AE (TEAE) if started after first dose administration and no later than last dose date + 30 days.

The event counts, the number, and percentage of subjects reporting TEAEs in the treatment group of the antecedent DB study and overall will be tabulated by system organ class (SOC) and preferred term; by SOC, preferred term, and maximum severity; and by SOC, preferred term, and relationship to study drug. If more than one TEAE occurs with the same preferred term for the same subject, then the subject will be counted only once for that preferred term using the most severe and most related occurrence for the summarization by severity and by relationship to study drug. The display in these tables will be sorted alphabetically by SOC and then by descending subject frequency for the preferred terms (combined counts from overall group) within each SOC.

The event counts, the number and percentage of subjects with any TEAEs will also be tabulated by preferred term without SOCs. This table will be sorted by descending subject frequency.

The incidence of most frequently reported (preferred terms reported by  $\geq 5\%$  of subjects overall) TEAEs, SAEs reported after treatment start, TEAEs leading to drug withdrawn, and TEAEs related to study drug will be summarized by SOC and preferred term. The tables will be sorted alphabetically by SOC and then by descending frequency within each SOC in overall group. In

addition, the incidence of fatal treatment-emergent AEs (i.e., events that cause death) will be summarized separately by SOC and preferred term.

These summary tables except for the most frequently reported TEAEs tables will also be presented by relationship to COVID-19 related Infection (Not related to COVID-19 Infection vs. Related to COVID-19 Infection).

An AE listing by subject will display all events, including those which are not treatment-emergent, and will include the verbatim term in addition to the MedDRA SOC and preferred term. This listing will also include all relevant eCRF data associated with the event: date of onset, date resolved, date of last dose, severity, frequency, outcome, relationship to study drug, and action taken with study drug. Separate listings will be presented for treatment-emergent SAEs, related TEAEs, TEAEs leading to drug withdrawn, fatal TEAEs (if any), and TEAEs Related to COVID-19 Infection.

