2 STUDY OBJECTIVES AND ENDPOINTS

2.1 Primary Objective

The primary objective of this study is to investigate the safety and tolerability of continued long-term treatment with oral trofinetide in girls and women with Rett syndrome.

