7 ADVERSE EVENTS

7.1 Specification of Safety Parameters

7.1.1 Definition of Adverse Event

An AE is defined as “any untoward medical occurrence in a patient or clinical study participant, temporally associated with the use of study drug, whether or not considered related to study drug”.

An AE can therefore be any unfavorable and unintended sign (e.g., an abnormal laboratory finding), symptom, or disease temporally associated with the use of a drug, without any judgment about causality or seriousness. An AE can arise from any use of the drug (e.g., off-label use, use in combination with another drug) and from any route of administration, formulation, or dose, including an overdose.

A suspected adverse reaction is any AE for which there is a reasonable possibility that the drug caused the AE.

AEs do not include the following:

- Stable or intermittent chronic conditions (such as myopia requiring eyeglasses) that are present prior to Baseline and do not worsen during the study

- Medical or surgical procedures (e.g., surgery, endoscopy, tooth extraction, transfusion). The condition that leads to the procedure is an AE if not present at Baseline.
- Overdose of concomitant medication without any signs or symptoms unless the subject is hospitalized for observation; if an overdose occurs, it will be reported on an overdose form
- Hospitalization for elective surgery planned prior to study (situation where an untoward medical occurrence has not occurred)
- Pregnancy will not be considered an AE, but if it occurs, it will be reported on a pregnancy form

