7.2.3 Duration

The start and stop dates for AEs will be recorded using the following criteria:

- **Start:** Date of the first episode of the AE or date of significant sustained worsening in severity
- **Stop:** Date when AE either ceased permanently or changed in severity

For AEs of diarrhea, the start date and stop date of a decrease in severity will also be recorded.

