7.2.4 Frequency

The frequency of the AE should be indicated according to the following definitions:

- **Single:** Experienced once, without recurrence
- **Recurrent:** More than one discrete episode with the same severity

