9.5.2 Primary Analyses

Adverse events will be classified into standard terminology using the Medical Dictionary for Regulatory Activities (MedDRA). All AEs will be listed and TEAEs will be summarized by system organ class and preferred term. A TEAE is defined as an AE that started after the first administration of study drug and no later than the last administration of study drug plus 30 days. Summaries by maximum severity and by relationship to study drug will also be provided. Serious TEAEs, fatal AEs, and TEAEs leading to discontinuation will also be summarized.

Descriptive summary statistics for ECG, vital signs and body weight, and clinical laboratory parameters, including observed values and changes from Baseline, will be tabulated by timepoint. Additionally, categorical analyses will be conducted on the incidence of subjects with prolonged QTc intervals and changes in QTc intervals in accordance with International Council for Harmonisation (ICH) guidelines.

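### A non-serious AE carried over from ACP-2566-004 that does not worsen enters no AE summary table, so the TEAE endpoint understates the AE burden of continued treatment

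*SAP*

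**What the plan says.** The two documents agree on the definition. SAP 14.2: an AE "will be considered a treatment-emergent AE (TEAE) if started after first dose administration", with an upper limit of 30 days after the last dose. Protocol 9.5.2: "A TEAE is defined as an AE that started after the first administration of study drug and no later than" 30 days after the last dose. Neither has a clause for recurrence of an AE that began earlier.

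Three recording rules feed that definition:

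- **Start and stop dates (Protocol 7.2.3).** The start is the "Date of the first episode of the AE or date of significant sustained worsening in severity". The stop is the "Date when AE either ceased permanently or changed in severity".
- **Frequency (Protocol 7.2.4).** An AE is classed as recurrent when there is "More than one discrete episode with the same severity".
- **Rollover (Protocol 7.3).** An AE with onset before the first dose here is an AE of the antecedent study. If it is ongoing, it is carried over and recorded in this study until it resolves or the safety follow-up takes place.

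SAP 14.2 limits the incidence, severity, relatedness and drug-withdrawal summaries to TEAEs. Events that are not treatment-emergent appear in the by-subject listing. SAP 6 tabulates discontinuations by reason without reference to TEAE status.

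The primary objective (Protocol 2.1) is "to investigate the safety and tolerability of continued long-term treatment with oral trofinetide".

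**The concern.** The first dose in this study is an administrative boundary. Every subject has just completed the 40-week study ACP-2566-004 on trofinetide, and the assigned dose is the final dose from that study (Protocol 4.1 and 5.1.3.1). For a question about continued treatment, the AEs that began earlier and have not gone away are central, and the onset-based definition moves those out of the tables.

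The SAP already recognises that this study's baseline is on drug. For continuous measures, SAP 5.1 adds a second analysis against the ACP-2566-003 baseline. AEs have no counterpart.

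A similar gap affects a second primary endpoint. Withdrawals due to AEs are not restricted to TEAEs as an endpoint (Protocol 2.1.1, SAP 14.1), but the planned table by preferred term is. A subject withdrawn for a carried-over AE would be counted in disposition but would be missing from the table that says which AE it was.

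Diarrhea is the obvious case, since Protocol 1.3 reports it in 56% at 200 mg/kg BID against 4% on placebo in the second Phase 2 study. A low diarrhea TEAE rate here could be read as tolerance developing when it partly reflects where the start date falls.

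**Working it through.** **Check of the definition.** The plan gives no figure to reproduce on this point, so the rules were applied to example records. Let Day 1 be the first dose here and take Day 911, the Week 130 target in SAP Table 2, as the last dose. A record is a TEAE if it starts after the Day 1 dose and no later than Day 911 + 30 = Day 941.

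| Record | Start date under Protocol 7.2.3 | TEAEs | Count if each bout were judged separately |
|---|---|---|---|
| Open at rollover, no later bouts | Day -120 | 0 | 0 |
| Same, 1 later bout, same severity | Day -120 | 0 | 1 |
| Same, 10 later bouts, same severity | Day -120 | 0 | 10 |
| Same, 50 later bouts, same severity | Day -120 | 0 | 50 |
| Same, sustained worsening on Day 40 | Day 40 | 1 | not needed |

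While the record stays open and does not worsen, the number of later bouts makes no difference.

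**Where such an AE is visible**

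| Output | Included? |
|---|---|
| TEAE incidence, severity, relatedness and the table of terms at 5% or more (SAP 14.2) | No |
| TEAEs leading to drug withdrawal (SAP 14.2) | No |
| By-subject AE listing (SAP 14.2) | Yes |
| Discontinuation by reason (SAP 6) | Only if it ends participation, and without the preferred term |

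**Illustration of size.** The planned number is 180 x 0.85 = 153 (Protocol 9.3). The documents do not say how many subjects enter with an ongoing AE, so the shares below are assumptions, not estimates. No subject is counted in both groups.

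- Carried over unchanged, 5% to 30%: 0.05 x 153 = 7.65, taken as 8; 0.30 x 153 = 45.9, taken as 46.
- New onset 3%: 0.03 x 153 = 4.59, taken as 5. New onset 10%: 0.10 x 153 = 15.3, taken as 15.

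| New onset | TEAE table shows | Affected on treatment, 8 carried over | Affected on treatment, 46 carried over |
|---|---|---|---|
| 5 | 5/153 = 3.3% | 13/153 = 8.5% | 51/153 = 33.3% |
| 15 | 15/153 = 9.8% | 23/153 = 15.0% | 61/153 = 39.9% |

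The table of frequent terms needs 0.05 x 153 = 7.65, so 8 subjects. In the first row the term drops out of it, although at least 13 subjects are affected.

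**The case against.** The strongest reply is that an onset-based definition is consistent across both documents, and that Protocol 7.3 deliberately assigns earlier-onset AEs to ACP-2566-004. How that study tabulates them cannot be seen here. The carried-over events are also recorded and listed, with severity, frequency, relationship and action taken. All of that stands, and it means the gap is in tabulation, not in data collection. It does not close the gap: an onset count in the earlier study cannot show who still had the event after rollover, and a listing gives no rate.

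A reader might go further in three ways that the documents do not support.

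- **That such an AE can never become a TEAE.** Significant sustained worsening gives a new start date. If a site closed the record before a new bout, Protocol 7.3 lets that bout be entered as an AE of this study. An unclear onset is counted as treatment-emergent (SAP 5.8). The protocol sets no symptom-free interval for permanent cessation, so sites may differ. For diarrhea, Protocol 7.2.3 also asks for dates of a decrease in severity, without saying whether that opens a new record.
- **That the primary endpoint as a whole misses persistent intolerance.** There are four primary endpoints. SAP 14.2 tabulates serious AEs reported after treatment start, and potentially clinically important changes, including weight change of 7% or more (SAP Table 7), do not depend on AE onset.
- **That Protocol 7.1.1 lets sites stop recording these events.** It excludes from AEs "Stable or intermittent chronic conditions (such as myopia requiring eyeglasses) that are present prior to Baseline and do not worsen during the study". The example is a background condition, and Protocol 7.3 specifically requires ongoing AEs from the antecedent study to be carried over. Stopping would breach 7.3, so no amendment to 7.1.1 is needed.

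**Conclusion.** The point holds for non-serious AEs whose record is still open at rollover and that continue or recur without worsening. These enter no AE summary table, and to that extent the TEAE endpoint understates how many subjects have AEs on continued treatment. The withdrawal table by preferred term has the same limit.

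The size cannot be estimated from the documents. The understatement is nil if no such AE is carried over, and the percentages above only show how it scales. The 56% diarrhea figure is no substitute: it counts events over a short Phase 2 double-blind period, not prevalence after 40 weeks in subjects who completed ACP-2566-004 and whom the investigator could exclude for AEs there (Protocol 4.2).

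This is a recommended addition to the analysis. It does not make the TEAE tables wrong for what they count, which is new onset and worsening.

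**What to change.** In SAP 14.2:

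1. Beside the TEAE tables, add a table by system organ class, preferred term and maximum severity of all AEs active at any time from the first dose in this study to 30 days after the last dose. Show AEs ongoing at first dose in a separate column. Add a note that an open recurrent record does not show when its bouts occurred, so the column counts active records and not dated episodes.
2. Tabulate all AEs leading to drug withdrawal by preferred term, whatever their onset date, so that the table matches the primary endpoint.

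If a clarification is wanted, state that the carry-over rule in Protocol 7.3 governs AEs that began on trofinetide in an antecedent study.

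The cost is one or two extra tables from records that Protocol 7.3 already requires, with no new data collection. The tabulated AE burden will look less favourable.

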Seizures are common, although not diagnostic. Commonly observed symptoms include awake breathing disruptions, scoliosis, and interest in social interaction (intense eye communication) (Neul et al. 2010; Percy et al. 2010). Gastrointestinal symptoms, including constipation and chewing and swallowing difficulties, are observed in the majority of patients with RTT (Motil et al. 2012). Sudden changes in mood, screaming and inconsolable crying are common behaviors in children and adolescents with RTT (Mount et al. 2001, 2002; Robertson et al. 2006; Cianfaglione et al. 2015). These impairments can further exacerbate

other symptoms and disrupt activities of daily living including educational, recreational and treatment opportunities (Epstein et al. 2016; Perry et al. 1991; Thompson and Iwata 2001; Iemmi et al. 2016). Autonomic manifestations, which include abnormalities in cardiac and respiratory function, as well as in peripheral circulation, are considered to be predominantly of central nervous system origin. Rett syndrome is also characterized by impaired growth affecting the brain and other organ systems.

Loss of purposeful hand use is a defining aspect of RTT during the onset of regression and at least 30% of individuals remain without any type of purposeful hand use (Downs et al. 2010). Individuals with some purposeful hand movements vary in their level of ability to reach for and grasp objects. The ability to self-feed is observed in 25-43% (Cass et al. 2003; Larsson et al. 2005; Downs et al. 2011). Poorer levels of hand function are associated with both age and severity of mobility impairment (Downs et al. 2011).

In adulthood, a late motor deterioration stage occurs, characterized by worsening dystonia, rigidity, and in some cases deterioration in the ability to walk and parkinsonian symptoms. Affected individuals have a yearly death rate between 1% and 2%, with 25% of all deaths characterized as sudden and unexpected (Kerr et al. 1997; Samaco and Neul 2011). Women with RTT can survive into their fifties and occasionally longer (Samaco and Neul 2011).

There are no medicines approved for the treatment of RTT. Treatment focuses on the management of each patient's symptoms and, even in that regard, is often unsatisfactory and has only a limited effect on functional improvement. Accordingly, the burden on families and other caregivers is very great (Palacios-Ceña et al. 2018).

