### **3. STUDY DESIGN**

#### **3.1 General Study Design**

This is a multi-center, open-label, long-term study of trofinetide to monitor the safety and efficacy of continuing trofinetide therapy. Subjects who complete the preceding open-label study (ACP-2566-004) will be eligible to enroll in the present study.

[figure not shown]
The duration of participation for individual study subjects will be approximately 32 months, or less than 32 months if: 1) trofinetide becomes commercially available for the treatment of Rett syndrome or 2) if development of trofinetide for Rett syndrome is discontinued. The Sponsor may discontinue the study for any reason. Note that not all subjects entering the present study will be treated for 32 months. It is anticipated that the time from which the first subject enters the present study until the predicted time that trofinetide receives marketing authorization and is marketed will be 29 months. Therefore, subjects who enter the present study, for example, 6 months after the first subject enters, will receive treatment with trofinetide for approximately 23 months before the study is terminated based on the anticipated date of commercial availability of trofinetide.

Legally acceptable representatives (LARs)/subjects must be consented prior to the procedures being performed at the end of treatment (EOT) visit of the antecedent study. The EOT visit of the antecedent study will serve as the Baseline visit of the present study. The data gathered at the EOT visit of the antecedent study serves as the baseline data of the present study. The duration of participation for individual study subjects will be up to approximately 32 months with a safety follow-up period of 30 (+4) days. Approximately 28 sites will participate in this study.

The study will have two periods ([Figure 1](#)):

- Treatment period: up to approximately 32 months
- Safety follow-up period: 30 days

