### **10.1 Exposure to Study drug**

Duration of exposure to study drug will be calculated for each subject as (last dose date – first dose date + 1). The number and percentage of subjects within each of the following exposure levels in terms of duration of exposure will also be tabulated: <12 weeks (1 to 83 days), 12 to <52 weeks (84 to 363 days), 52 to <104 weeks (364 to 727 days), 104 to <130 weeks (728 to 909 days), and >=130 weeks (910 days or longer).

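### The primary adverse event tables give only counts and crude percentages although planned exposure differs between subjects; adding rates per subject-year and incidence by time on drug would be a cheap improvement

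*SAP*

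**What the plan says.** Safety and tolerability of long-term treatment is the only primary objective (Protocol 2.1, SAP 2.1). Treatment-emergent adverse events (TEAEs), serious events and withdrawals due to adverse events are among the primary endpoints (Protocol 2.1.1, SAP 14.1).

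SAP 14.2 tabulates "The event counts, the number, and percentage of subjects reporting TEAEs in the treatment group of the antecedent DB study and overall" by system organ class and preferred term, and again by maximum severity and by relationship to study drug. A further table uses the same measures: "The event counts, the number and percentage of subjects with any TEAEs will also be tabulated by preferred term without SOCs". Common TEAEs (at least 5% of subjects), serious events, TEAEs leading to withdrawal of drug, related TEAEs and fatal TEAEs are summarised as incidence by class and term. Protocol 9.5.2 plans summaries of the same kind, and SAP 14.7 states that there are no further safety endpoints.

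An event counts as treatment-emergent if it "started after first dose administration and no later than last dose date + 30 days", so the window lengthens with each subject's own exposure. On exposure, SAP 3.1 says: "Note that not all subjects entering the present study will be treated for 32 months". It anticipates 29 months from first entry to marketing, and says that a subject entering 6 months later "will receive treatment with trofinetide for approximately 23 months before the study is terminated". SAP 10.1 derives the needed quantity ("Duration of exposure to study drug will be calculated for each subject as" last minus first dose date plus one) and groups subjects into five bands from under 12 to at least 130 weeks. No adverse event table draws on it.

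**The concern.** A crude percentage has one unit per subject in its denominator, however long that subject was observed. Where observation time differs by entry date and by withdrawal, the percentage reflects both the risk and the follow-up. Three readings that a long-term safety study should support then become difficult:

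- Comparison with the antecedent studies, which ran for 12 and 40 weeks (Protocol 1.4).
- Comparison with the background death rate in Protocol 1.1, which is given per year (1% to 2%).
- Whether risk falls, persists or emerges late with time on drug.

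SAP 15 adds a further occasion for unequal follow-up: an interim data cut if a marketing application is submitted before the study ends. Late entrants would have less time still at that cut.

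**Working it through.** **Figures in the plan.** 180 × 0.85 = 153 subjects (SAP 3.4) and 29 − 6 = 23 months (SAP 3.1). Both reproduce. There is no power or error rate to reproduce, because the study is descriptive (Protocol 9.2).

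**Search for a time-based measure.** Protocol 9.5.2 and SAP 10.1, 14.2 and 14.7 contain no event rate per unit of time, no time to first event and no incidence by interval.

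**Effect of follow-up alone.** The documents give no event rates for this study, so the rates here are assumptions. With a constant first-event rate r per year and m months observed, the expected percentage with an event is 1 − exp(−r × m/12).

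| Assumed rate per year | 23 months | 29 months | Ratio |
|---|---|---|---|
| 0.1 | 1 − exp(−0.192) = 17.4% | 1 − exp(−0.242) = 21.5% | 1.23 |
| 0.3 | 1 − exp(−0.575) = 43.7% | 1 − exp(−0.725) = 51.6% | 1.18 |

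The 30-day tail adds about one month to each time (24.0 and 30.0 months). At 0.1 per year this gives 18.1% and 22.1%, a ratio of 1.22, so the picture is unchanged.

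**The same in reverse.** A crude 30% corresponds to −ln(0.7)/(23/12) = 0.186 per year over 23 months and −ln(0.7)/(29/12) = 0.148 per year over 29 months.

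**Whole study.** Neither the accrual period nor the dropout rate is given. Assume uniform entry over 6 to 18 months, a common stop 29 months after first entry, and dropout of 0 to 0.5 per year. Simulation then gives mean exposure of about 13 to 26 months, or about 170 to 332 subject-years for 153 subjects. (Check of the upper end: entry over 6 months without dropout has mean 29 − 3 = 26 months, and 153 × 26/12 = 332.) Over that range one unchanged rate produces these crude percentages:

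- 0.1 per year: 10.3% to 19.5%
- 0.25 per year: 23.3% to 41.8%

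**Deaths.** Under the same assumptions, a crude 2.2% of 153 subjects is 3.4 deaths. Over 332 subject-years that is 3.4/332 = 1.0% per year; over 170 it is 3.4/170 = 2.0% per year. The crude percentage alone cannot say which end of the range in Protocol 1.1 it matches.

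**The case against.** The strongest reply is that nothing here is broken. The protocol promises descriptive summaries and the SAP delivers them. No test, decision rule or error rate depends on the choice, and a subject percentage correctly describes who ever reported an event. Exposure is also reported as a continuous variable (SAP 10), event counts are tabulated, and the adverse event listing shows onset and last-dose dates (SAP 14.2). A reader can multiply the number of subjects by mean exposure and obtain an overall event or death rate. All of this stands. That rough rate leaves out the 30-day tail, however. It gives neither a first-event rate for a given term nor the number at risk in each period.

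Four stronger readings that a reader might infer are not supported:

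- *The same risk could show as a two-fold difference.* That needs 12 versus 29 months (9.5% versus 21.5% at 0.1 per year). The documents give no source for 12 months of exposure; their own example is 23 versus 29. Early withdrawal could widen the gap, but no rate is stated.
- *Between 3.7 and 7.4 deaths would be expected.* This is 153 × 29/12 × 1% to 2%, which takes 29 months as the mean. In SAP 3.1 it is the anticipated time for the first entrant, so with staggered entry and a common stop at that date the mean must be lower.
- *The former treatment groups will be biased against each other.* All subjects receive trofinetide here, and both groups followed the same 12-week and 40-week path. Differential dropout could separate them, but none is documented and no between-group test is planned.
- *Comparison with the yearly death rate is impossible.* It is not direct, but the rough overall rate permits it.

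**Conclusion.** The point holds as an improvement to the plan, not as the correction of an error. The primary adverse event tables carry no measure of time although unequal exposure is planned and already derived for each subject. On the exposure times in the plan, the distortion is about 1.2-fold (roughly 4 percentage points at 0.1 per year and 8 at 0.3). This assumes a constant rate, and the rates themselves are assumed. Withdrawal would add to it by an amount that the documents do not allow anyone to state. The larger loss is that the planned tables do not show how risk changes with time on drug, which is central to a long-term safety study.

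**What to change.** Keep the crude tables. In SAP 14.2 add the following for any TEAE, serious events, TEAEs leading to withdrawal, deaths, and preferred terms reported by at least 5% of subjects:

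- (a) Subjects with a first event per 100 subject-years. Time at risk ends at the first event or at the end of observation. End of observation is last dose plus 30 days, or the last contact or the start of commercial trofinetide if earlier.
- (b) Events per 100 subject-years of observation, counting only events within that time.

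The earlier stopping points matter because subjects who complete and start commercial product within 30 days have no scheduled follow-up contact (Protocol 3.1.2), so part of their tail is not reliably observed.

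For the commonest terms, show incidence by time since first dose in this study, with the number at risk in each interval. Use the SAP 10.1 cut points: under 12, 12 to under 52, 52 to under 104, 104 to under 130, and at least 130 weeks. The last two may be pooled: 130 weeks is 130 × 7/365.25 × 12 = 29.9 months, beyond the 29 months anticipated for the first entrant. These should be periods of follow-up, not groups of subjects by total exposure.

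State also that a subject with a carried-over ongoing event (Protocol 7.3) is not at risk of new onset of that term until it resolves. Otherwise the earliest interval would include people who could not have a new onset, and early incidence would look too low.

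The cost is SAP wording and a few extra tables from dates already collected; no visit or procedure changes. A single rate assumes a roughly constant hazard, and the interval table is there to show where that fails.
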